11.0 Statistical/Data Analysis Plan

11.1 Statistical Considerations:

List the statistical methods to be used to address the primary and secondary objectives, specific aims, and/or research hypotheses. Explain how missing data and outliers will be handled in the analysis. The analysis plan should be consistent with the study objectives. Include any sub-group analyses (e.g., gender or age group). Specify statistical methods and variables for each analysis. Describe how confounding variables will be controlled in the data analysis

The Primary outcome for this study is the measure of perceived pain intensity with and without the use of the VR headset. The outcome will be measured with the VAS scale for pain which will be completed immediately after each procedure. The VAS will be measured as a 100 mm line on which the participant will be instructed to make a mark corresponding to their level of pain. The mark will then be measured with a metric ruler and the appropriate number documented.

A 13 mm change is the minimum clinically significant difference that is noticeable by patients according to a study by Gallagher et al 2001. **The null hypothesis in this study is that the average pain intensity between groups will be not be clinically significant, which is defined as 13mm.**

The primary statistical method will be to measure the mean perceived pain between groups using the VAS. The t-test will be used to determine if the effect size between the two groups is statistically significant as this is a study with a dichotomous predictor variable (with or without VR) but a continuous outcome variable (pain measurement on the VAS).

Additional outcomes to include satisfaction with the procedure and likelihood of requesting VR again if it is available will be measured using the Likert scale. It will be measured on a one to five scale. Results of the Likert scales will be reported as is. Likert scale questions are as follows:

Overall, how satisfied were you with the use of Virtual Reality in reducing your pain level?

5	4	3	2	1
Very Satisfied	Satisfied	Not Sure	Unsatisfied	Very Unsatisfied

Overall, how satisfied were you with the use of Virtual Reality in reducing your anxiety level?

5	4	3	2	1
Very Satisfied	Satisfied	Not Sure	Unsatisfied	Very Unsatisfied

How likely would you be to request Virtual Reality if it were available for use for other painful or anxiety-inducing procedures?

5	4	3	2	1
Very Likely	Likely	Not Sure	Unlikely	Very Unlikely

As this study will utilize and Intention to Treat (ITT) methodology, all enrolled subjects will be included in the final data analysis.

11.2 Sample Size:

60

11.3 Total number of subjects requested (including records and specimens):

60

11.4

If you are recruiting by study arm, please identify the arms of the study and how many subjects will be enrolled in each arm

Control (standard of care) - 30

Experimental (standard of care plus virtual reality) - 30

11.5 Please provide a justification for your sample size

A study performed by Todd et al 1995 and a later validation study by Gallagher et al 2001 both found that a minimum clinically significant change in pain as measured on the VAS is 13mm. Both studies found that the change in pain reported as "a little more pain" or "a little less pain" after intervention averaged to 13mm. Both studies also found that the standard deviation of change in pain reported on the VAS as "a little more pain" or "a little less pain" was 17mm.

Since the t-test will be used at the end of the study to determine if the effects are statistically significant, the E/S ratio (expected effect size divided by the standard deviation of the outcome variable) was used to determine the sample size. The E/S ratio is being estimated based on the studies cited above. The expected effect size (13mm) divided by the standard deviation (17mm) =0.76. To ensure a 2-sided α 0.05 and β 0.20, a minimum of 27 subjects are required for each arm. This is based on a sample size calculator created by Dhand et al as well as appendix 6A of *Designing Clinical Research* authored by Hulley et al.

Although a total of only 54 participants is required for this study to be effectively powered, we're requesting 60 to account for a potential dropout rate of 10%.

Minitab software will be utilized for final data analysis.

11.6 Data Analysis Plan: Complete description: Background, Objectives, Design, Step by Step how the project is going to be done, Data analysis plan:

The primary outcome be measured as the average pain rating between the two groups as measured on the VAS. The t-test will be used to compare the two groups to determine if the difference is statistically significant. The difference between the two groups should be at least 13mm to be considered clinically significant.

The preprocedural anxiety will also be measured using the VAS and the average difference will be reported in the data, although a minimum clinically significant score is not available.

Since participants will be randomly assigned to each study arm, it will be impossible to insure an even spread of ages between the two study arms. It may be possible that pain perception changes with age, and since this study will include ages 18-50, data tables comparing the average changes between those in different age groups (i.e. 18-25, 26-33, 34-41, 42-50). A separate subgroup analysis will be performed comparing different age subgroups.

Similar data analysis will be included for pre-procedural anxiety.

Likert scale questions ("Overall, how satisfied were you with the use of Virtual Reality?" and "How likely would you be to request Virtual Reality if it were available for use?") will be reported in the final manuscript.

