A prospective randomized controlled trial comparing standard practice for conducting venipuncture to standard practice with the addition of Virtual Reality using the Oculus Go Head Mounted Display (HMD). The study will be performed on volunteers who are reporting to the phlebotomy lab to have venipuncture for blood draws that were previously ordered by their health care providers. Participants who were not already scheduled to undergo routine venipuncture will not be included.

[figure not shown]
When approaching the ticket stand to draw a waiting number for the lab, prospective participants will be asked by an assistant investigator located near the kiosk if they are interested in participating in the study. If the participants express interest, they will be directed to the screening station. The screening station will be set up in a private room near the lab waiting area, and participants will be screened for eligibility and educated on the benefits and risks of the study. They will also provide informed consent if they decide to participate.

All participants will be asked to fill out a self-reported data questionnaire in addition to the informed consent document to assess for inclusion and exclusion criteria discussed later in this protocol. This questionnaire will assess the participant's expected level of anxiety prior to the procedure and expected level of pain associated with the procedure by utilizing a visual analog scale (VAS). The VAS will be on a 100 millimeter line similar to the one shown below:

Expected level of **Anxiety** before having blood drawn

Expected level of **Pain** with needle insertion for blood draw

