Once approved for participation in the study all participants will undergo a brief instructional class on how to operate the HMD and will be allowed sufficient time to become comfortable with its use. We expect approximately 5-10 minutes to be required for this portion of the study. Once familiar with the use of the VR headset, participants will be asked to randomly draw an envelope from a container. This envelope will contain a block and sequence number. The block and sequence number will be the subject ID and will correspond to a predetermined number set on a separate document that will determine if the participant will use the HMD during venipuncture or not. The screener will not have immediate access to the list showing which group the participant will be assigned to. One member of the study team will be present in the lab room to ensure the participant uses the VR headset (or not) according to what is randomly drawn. This member of the research team will have the list showing whether or not the participant is assigned to the control arm or the experimental arm. The participants will then proceed to the specimen room to undergo venipuncture.

Venipuncture for both groups will occur in the non-dominant arm. The reasoning for this is that the Oculus Go requires one free hand to use a controller. This will ensure that the individuals participating are able to effectively use the device. Those unable to undergo venipuncture in the non-

dominant arm will undergo venipuncture in the dominant arm instead and will use the Oculus Go controller with their non-dominant hand.

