---------------------	----------------	---------------	------------------	-----------------------

How likely would you be to request Virtual Reality if it were available for use for other painful or anxiety-inducing procedures?

5 Very Likely	4 Likely	3 Not Sure	2 Unlikely	1 Very Unlikely
------------------	-------------	---------------	---------------	--------------------

10.2 Data Collection:

Describe all the data variables, information to be collected, the source of the data, and how the data will be operationally measured.

The independent variable for this study is the use of VR or lack thereof. The dependent variables include accurately measuring anxiety levels pre and post procedure, pain levels after the procedure, and satisfaction with the procedure in regards to pain control, anxiety management, and ease of use. The participant's gender, age, and a minimal medical history will be obtained for purposes of inclusion or exclusion from the study. The information collected relevant to the conduct of the study will include any history of bloodborne disease, anxiety, seizures, pregnancy status, right vs left handedness, VR experience, nausea, vomiting, or vertigo. Participants will also be asked to rate their expected pain and anxiety associated with venipuncture using the Visual Analog Scale (VAS). The above information will be collected on the self-reported data sheet prior to providing specimens. The questionnaires will also enquire as to whether the participant took any pain medications prior to arrival, as well as rate pre and post-procedure anxiety level on a VAS scale. Finally, patients will then rate their procedure related pain intensity on the VAS scale.

Participants will also be asked about their satisfaction level with the use of VR in regards to pain control, anxiety management, and ease of use and their likelihood of requesting VR if available in the future using the Likert scale. All information will be provided and data collected voluntarily, and participants may choose not to answer any questions they choose.

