possession of the PI. When not in the PI's possession it will be secured in a locked office. The de-identified electronic data will be stored on the attached Excel spreadsheet. Paper copies will be shredded once data has been transferred. Once the study is complete the electronic documents will be maintained on the primary investigator's CAC-enabled/password protected government computer until the computer is turned in upon PCSing and then deleted.

14.4 Potential Benefits:

Describe any real and potential benefits of the research to the subject and any potential benefits to a specific community or society

If the individuals in the research are considered experimental subjects (per 10 USC 980), and they cannot provide their own consent, the protocol must describe the intent to directly benefit all subjects

The subjects in the experimental group will potentially benefit from this study via reduction in anxiety and pain control, but will not directly benefit from this study in any other way. If Virtual Reality is shown to decrease pain intensity and anxiety levels with venipuncture, it may be offered in the lab setting, clinic setting, emergency room setting, or deployed setting to improve the care that can be provided.

14.5 Privacy for Subjects:

Describe the measures to protect subject's privacy during recruitment, the consent process, and all research activities, etc.

During the screening process no PHI will be collected. The participant's name and signature will be on the consent form, but will not be linked to any PHI. The screening questionnaire will contain age and gender, and will ask several questions about health, but will not be linked to the consent form and therefore will not contain PHI. This will be performed in a private room with only the member of the study team collecting the data present. Once gathered, the data will be stored in electronic form on a secure CAC-enabled/password protected government computer that will be in the possession of the PI. After paper documents are transferred electronically they will be shredded, the electronic documents will be kept for 3 years and then deleted.

14.6 Incidental or Unexpected Findings:

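### The primary pain comparison ignores expected pain and age, both recorded before randomisation, and the age imbalance that the plan itself raises is left to a subgroup analysis with no stated method.

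*Combined protocol and SAP*

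**What the plan says.** - **Primary analysis.** Sections 11.1 and 11.6 name a two-group t-test on post-procedure VAS pain: "The t-test will be used to compare the two groups to determine if the difference is statistically significant". No covariate, ANCOVA or regression model appears anywhere in the plan.
- **Baseline data.** Under section 10.1 the screening questionnaire records the "expected level of anxiety prior to the procedure and expected level of pain associated with the procedure by utilizing a visual analog scale". Section 14.5 adds: "The screening questionnaire will contain age and gender".
- **Timing.** Allocation comes after screening and headset training (section 10.1): "Once familiar with the use of the VR headset, participants will be asked to randomly draw an envelope from a container". Expected pain and age are therefore true pre-randomisation covariates.
- **Age.** Section 11.6 says "it will be impossible to insure an even spread of ages between the two study arms" and allows that pain perception may vary with age. Its response is tables in four bands (18-25, 26-33, 34-41, 42-50) and this sentence: "A separate subgroup analysis will be performed comparing different age subgroups". No test, model, interaction term or alpha is given.
- **Confounding.** The prompt in section 11.1 asks the authors to "Describe how confounding variables will be controlled in the data analysis". The reply contains no adjustment method. The closing lines of section 11.6 extend similar analysis to pre-procedural anxiety and add no adjustment either.

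**The concern.** A subgroup analysis by age asks whether the VR effect differs between age groups. It does not correct the overall arm difference for a chance imbalance in age. The plan therefore names a problem and answers it with a tool that addresses a different question. Meanwhile a rating of the same needle stick, on the same type of 100 mm scale as the outcome, is collected before allocation and left out of the pain comparison.

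Three things are at stake:

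- precision that may be available from data already on the form;
- a pre-specified answer if the arms do differ in age or expected pain (without one, any adjusted estimate would be chosen after the data are seen);
- the open wording of the subgroup analysis, which would allow several very small within-band tests.

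**Working it through.** **Inputs from the plan (sections 11.4 and 11.5).** Difference 13 mm, SD 17 mm, two-sided alpha 0.05, power 80%, 27 per arm evaluable, 54 in total, 60 enrolled (30 per arm) to allow for 10% dropout.

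**Assumptions.** Section 11.5 describes 17 mm as the SD of a change in pain; here it serves as the SD of the post-procedure score, and 20 mm is also tried. R is the multiple correlation of expected pain and age with reported pain. The documents do not give it, so a range is shown.

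**1. The plan's own figure.** n per arm = 2 × [17 × (1.960 + 0.842) / 13]² = 26.8, rounded up to 27; 54 / 0.90 = 60. The stated sizes reproduce by the normal approximation. The exact noncentral-t calculation gives 78.7% power at 27 per arm and 83.0% at 30. The sample size is not in dispute.

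**2. Power with adjustment (k = 2 covariates).** Residual SD = 17 × √(1 − R²); for example, R = 0.5 gives 14.72 mm. Degrees of freedom = 2n − 4. Noncentrality = 13 / [residual SD × √(2/n)] × √(1 − r²), where r² is the chance association between arm and covariates, distributed Beta(k/2, (2n − 1 − k)/2). Power is averaged over r², which charges ANCOVA for chance imbalance as well as for the lost degrees of freedom.

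| Per arm | SD (mm) | Unadjusted | R = 0 | R = 0.2 | R = 0.3 | R = 0.5 | R = 0.6 |
|---|---|---|---|---|---|---|---|
| 27 | 17 | 78.7% | 77.1% | 78.7% | 80.8% | 87.7% | 92.1% |
| 30 | 17 | 83.0% | 81.6% | 83.1% | 85.0% | 91.0% | 94.7% |
| 30 | 20 | 69.7% | 68.1% | – | 72.2% | 80.1% | – |

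At SD 17 mm the break-even R is 0.20 at 27 per arm and 0.19 at 30. A simulation of 40,000 runs agrees: 0.770, 0.807 and 0.878 at 27 per arm, and 0.816, 0.853 and 0.910 at 30, for R = 0, 0.3 and 0.5.

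**3. Precision at 30 per arm, SD 17 mm.** The mean 95% CI half-width is 8.79 mm unadjusted, against 8.95 mm (R = 0), 8.54 mm (0.3) and 7.75 mm (0.5).

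**4. What a chance imbalance can do.** As an illustration, take a covariate correlated 0.5 with pain that differs between arms by 0.5 SD. At 30 per arm this has a two-sided chance of about 5%. It shifts the unadjusted difference by 0.5 × 0.5 × 17 = 4.3 mm.

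**5. The age bands.** These figures apply only if the subgroup analysis means a t-test in each band and ages are evenly spread. Then 60 / 4 = 15 per band, or 7 to 8 per arm. Power for 13 mm is 26% at 7 per arm and 30% at 8. Four tests at 0.05 carry a 1 − 0.95⁴ = 18.5% chance of at least one false positive.

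**6. An interaction instead.** At 30 per arm the standard error of the arm difference in age slope, per SD of age, is 17 × √(2/30) = 4.39 mm. The slope difference detectable with 80% power is about 12.5 mm per SD of age, so this analysis can only be exploratory.

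**The case against.** The strongest reply is that this is analyst preference. The t-test is valid under randomisation, sections 11.1, 11.5 and 11.6 use it consistently, and the trial is sized for it. On the plan's own inputs the enrolled 30 per arm give 83.0% power, above target. The gain depends entirely on R, which nobody has. Expected pain is an anticipatory rating, not a baseline value of the outcome, and at R = 0.3 the gain is only about 2 points. The confounding sentence is a generic form prompt. The primary test is fixed in advance, so it carries no covariate flexibility. The within-band figures depend on a reading that the plan does not state, and the proposed interaction is itself weak.

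Most of these statements are correct and limit the claim: there is no bias, no wrong sample size and no guaranteed gain. They do not remove it. The primary test is fixed, but the plan has no adjusted estimate for the imbalance that it foresees, so any such estimate would be post hoc. The 83.0% assumes no dropout; at the 27 per arm that the plan requires, exact power is 78.7%.

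A further objection is linkage. The subject ID comes from an envelope drawn after the questionnaire, and the documents do not say that the earlier form carries it. However, the planned age-band tables already require age to be joined to outcome, so ANCOVA adds no new requirement. Stating the link explicitly would still be sensible.

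**Conclusion.** The concern holds, as a change that should be made rather than an error that invalidates the trial. The plan leaves out two pre-randomisation covariates and gives no pre-specified adjusted estimate, although it expects that ages may be uneven. With a 13 mm difference and SD 17 mm, adjusting costs 1.4 points of power (30 per arm) to 1.7 points (27 per arm) if the covariates predict nothing. It gains 8.0 to 9.0 points at R = 0.5. If the SD is 20 mm, the R = 0.5 gain at 30 per arm is 10.4 points (69.7% to 80.1%). Confidence is medium, because R is unknown and the 17 mm SD is borrowed from change scores. The subgroup power and false-positive figures are conditional on within-band testing and an even age spread.

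**What to change.** In sections 11.1 and 11.6:

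1. Pre-specify as primary an ANCOVA of post-procedure VAS pain on arm, with expected-pain VAS and continuous age as covariates.
2. Add a rule for a missing covariate, for example the overall mean across both arms, so that every enrolled subject with a pain outcome stays in the model. The rule is needed because section 10.2 says "participants may choose not to answer any questions they choose", while section 11.1 commits to analysing all enrolled subjects.
3. Keep the unadjusted t-test as a sensitivity analysis.
4. Replace the age subgroup comparison with one arm-by-continuous-age interaction, labelled exploratory and reported as an estimate with its confidence interval. Keep the band tables as description.
5. State that the screening form carries the subject ID.

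The cost is SAP wording, with no new data. The model uses two degrees of freedom, and its worst-case loss is the 1.4 to 1.7 points of power shown above.

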Given the lack of research on the use of VR with common procedures such as IV access in an adult population, it remains unclear whether the use of VR would be beneficial in this population, or if the benefits are limited only to pediatric patients. If the results of this study show significant improved pain and anxiety levels in adults, thus rejecting the null hypothesis (which is that there will be no significant difference in pain or anxiety with and without the use of virtual reality), it would be reasonable to initiate further research into the use of VR for other common procedures performed in the emergency department, laboratory, family practice, or in the military setting while deployed.

9.3 Objectives/Specific Aims/Research Questions:

Describe the purpose and objective(s) of the study, specific aims, and/or research questions/hypotheses

The study's primary outcome is to determine if the use of immersive virtual reality with the Oculus Go improves the patient's pain ratings and pain intensity levels when undergoing venipuncture during routine blood draws versus the standard practice. We will use the Visual Analogue Scale (VAS) for pain assessment after each blood draw.

The study's secondary outcome is to assess procedure related anxiety before and after each intervention, which will also be measured with the VAS. We will also use the Likert scale to measure participant satisfaction with the procedure and whether or not they would request the use of VR again if available.

9.4 Study Design:

Describe study design in one to two sentences (e.g., prospective, use of existing records/data /specimens, observational, cross-sectional, interventional, randomized, placebo-controlled, cohort, etc.). Specify the phase – Phase I, II, III, or IV – for FDA-regulated investigational drug research

This study is a prospective randomized controlled trial comparing the standard practice for venipuncture to the standard practice with the addition of Virtual Reality. In order to test our hypothesis, we will be conducting this study in the phlebotomy lab on patients aged 18-50 years old who are already undergoing venipuncture for routine lab testing.

The study will test the participant's acute pain level associated with the procedure, as well as testing their level of procedure-related anxiety before and after the procedure.

9.5 Target Population:

Describe the population to whom the study findings will be generalized

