Those utilizing the Oculus Go HMD will be interacting with the VR game Ocean Rift. They will utilize a single controller to explore an underwater safari park. Ocean Rift has multiple environments to choose from, including coral reefs, ship wrecks, lagoons, the arctic, and prehistoric seas. Participants may interact with and learn about different creatures to include dolphins, turtles, orcas, ray, whales, sea lions, manatees, and dinosaurs. During the game users may travel where they please and interact with what they choose. The VR device is equipped with head-tracking software that allows the user to choose direction by looking around. The entire interior and exterior of the headset will be cleaned with alcohol-based wipes after each use. Alcohol will be used since it is generally well-tolerated on human skin, and since it evaporates quickly. The headset will be dried in the open air for a minimum of two minutes between each subject's use.

Those not using the VR will still wear a headset that will simply be turned off. This is to ensure that any significant change noted with the VR is due to the use of VR itself, and not simply due to "blindfolding" the patient during the procedure.

As some patients experiencing anxiety may be tempted to move during the procedure, lab personnel will instruct participants to remain still during venipuncture. Participants will be advised that they may take breaks as needed if anxiety becomes overwhelming.

After undergoing the procedure, each participant will be asked to fill out the post-procedure questionnaire and return it to the study team member present in the lab room, who will clean the headset as the participant completes the questionnaire. This questionnaire assesses the patient's pain intensity and level of anxiety with the VAS similar to the VAS shown above, as well as the patient's satisfaction with the visit which will be measured utilizing a Likert scale for individual questions (see below).

Overall, how satisfied were you with the use of Virtual Reality in reducing your pain level?

5 Very Satisfied	4 Satisfied	3 Not Sure	2 Unsatisfied	1 Very Unsatisfied
---------------------	----------------	---------------	------------------	-----------------------

Overall, how satisfied were you with the use of Virtual Reality in reducing your anxiety level?

5 Very Satisfied	4 Satisfied	3 Not Sure	2 Unsatisfied	1 Very Unsatisfied

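### The post-procedure anxiety score, which the secondary outcome depends on, has no stated analysis; the plan names only pre-procedural anxiety

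*Combined protocol and SAP*

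**What the plan says.** **What is promised.** Section 9.3 gives the secondary outcome as "to assess procedure related anxiety before and after each intervention", measured on the VAS. The null hypothesis in section 9.2 is that "there will be no significant difference in pain or anxiety with and without the use of virtual reality". Anxiety is also in the trial title.

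**What is collected.** In section 10.1 the screening questionnaire records the "expected level of anxiety prior to the procedure and expected level of pain associated with the procedure by utilizing a visual analog scale". After the blood draw there is a second form: "This questionnaire assesses the patient's pain intensity and level of anxiety with the VAS". Section 10.2 lists anxiety before and after the procedure among the dependent variables and says the questionnaires will "as well as rate pre and post-procedure anxiety level on a VAS scale", with no timing.

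**What is analysed.** Section 11.1 gives methods for the pain VAS and the Likert items only, and ties the t-test to pain. Section 11.6 mentions the anxiety VAS twice: "The preprocedural anxiety will also be measured using the VAS and the average difference will be reported in the data", and, after the paragraph on age subgroups, "Similar data analysis will be included for pre-procedural anxiety". The form's instruction in section 11.1 is to "Specify statistical methods and variables for each analysis".

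**The concern.** The anxiety question is whether patients using VR are less anxious once the procedure is over than patients wearing a headset that is switched off. The score that answers it is the post-procedure VAS, which section 11 does not mention. The score that section 11 does mention is taken, as section 10.1 describes it, before anyone is allocated.

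Two things are at stake. An analyst who follows the text literally will report a baseline comparison as the anxiety result. An analyst who assumes something else was meant must choose the variable, the contrast and the method, and can do so after seeing the data. Both matter for an outcome that the trial presents as its main secondary result.

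**Working it through.** **1. Order of events.** Section 10.1 places the expected-anxiety VAS on the screening questionnaire. The headset tutorial comes next, then the envelope draw, then venipuncture, then the post-procedure form. Section 13.1 also puts screening and tutorial before the envelope. The screening score X is therefore fixed before allocation, and under randomisation E[mean X (VR) − mean X (control)] = 0 for any VR effect.

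**2. Candidate readings of the average difference in section 11.6.**
- Between arms in X: expectation 0, so it carries no information about VR.
- Before to after, pooled or within arm: this is not a comparison between arms.
- Before to after, compared between arms: a valid estimate of the VR effect. However, the text states neither the post-procedure score, nor the contrast, nor a test.

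**3. Figures in the plan.** No sample size or detectable difference is given for anxiety. The only stated calculation is for pain: 2 × [17 × (1.96 + 0.84)/13]² ≈ 26.8, so 27 per arm, and 54/0.9 = 60. It reproduces and is not in dispute.

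**4. How much the choice matters.** Let Y be the post-procedure score. Assume X and Y have equal variances and correlation ρ. The documents give no ρ, so a range is shown. Relative variances of the between-arm estimate are:
- post-procedure score alone: 1
- change score: 2(1 − ρ)
- ANCOVA of Y on X: 1 − ρ²

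Hence change/ANCOVA = 2/(1 + ρ), post only/ANCOVA = 1/(1 − ρ²), information lost by the change score = (1 − ρ)/2, and the ANCOVA-equivalent size of a 60-person change-score analysis = 60(1 + ρ)/2.

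| ρ (assumed) | Change / ANCOVA | Information lost by change score | 60 by change score ≈ ANCOVA with | Post only / ANCOVA |
|---|---|---|---|---|
| 0.3 | 2/1.3 = 1.54 | 35% | 39 | 1/0.91 = 1.10 |
| 0.5 | 2/1.5 = 1.33 | 25% | 45 | 1/0.75 = 1.33 |
| 0.7 | 2/1.7 = 1.18 | 15% | 51 | 1/0.51 = 1.96 |

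A simulation with 30 per arm and a true effect of −0.6 SD gave a mean baseline difference of 0.00. Change score and ANCOVA both averaged −0.60, so both are unbiased. The variance ratios fell slightly below the formula values because ANCOVA estimates one extra slope.

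**5. In millimetres.** Take 30 per arm, a two-sided 5% t-test, 80% power and an assumed anxiety SD of 25 mm (none is given). The detectable difference on the post-procedure score alone is 18.4 mm. Multiplying by √[2(1 − ρ)] or √(1 − ρ²) gives:

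| ρ (assumed) | Change score | ANCOVA |
|---|---|---|
| 0.3 | 21.8 mm | 17.5 mm |
| 0.5 | 18.4 mm | 15.9 mm |
| 0.7 | 14.2 mm | 13.1 mm |

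The same trial could therefore detect anything from 13.1 to 21.8 mm, depending on a choice the plan leaves open and a correlation it does not give.

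**The case against.** The best defence is that the baseline-only reading is not what the authors meant. The same sentence in section 11.6 regrets that no minimum clinically significant anxiety score is available, which would be relevant only to a change or a treatment effect. The word preprocedural may be a slip for procedure-related. Section 11.5 says in general terms that a t-test will be used at the end of the study, and the promise of similar analysis could carry that test over to anxiety. The bolded null hypothesis in section 11.1 concerns pain alone, so the authors may have intended only a description of anxiety. Finally, the efficiency figures compare valid analyses under assumed correlations, and omitting ANCOVA is not in itself an error.

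Some of this stands. A before-to-after comparison is a plausible intention, a t-test is a possible reading, and the variance ratios are illustrative: they apply only if a change score or an unadjusted post-procedure score was intended. A wording slip is also possible, although the same term appears twice.

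None of it supplies the missing analysis. The t-test sentence sits in the pain sample-size justification. The promise of similar analysis follows the age-subgroup paragraph and again names pre-procedural anxiety. No sentence in section 11 names the post-procedure anxiety VAS or defines the difference. Even a purely descriptive report has to say which score is compared between which groups.

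Section 10.2 may simply be restating the two forms in section 10.1, so a second pre-procedure rating is only a possibility. It still needs ruling out, because sections 10.1 and 13.1 differ on whether the envelope reveals the arm.

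**Conclusion.** The concern holds. For the anxiety VAS, section 11 names the wrong variable twice, leaves the difference undefined and states no method for the score that would show a VR effect. On the literal reading the reported contrast has expectation 0. That conclusion rests only on the order of events in sections 10.1 and 13.1. On the reading most favourable to the plan, the analysis is unbiased but not prespecified. It also loses about 15% to 35% of the information relative to ANCOVA, assuming equal variances and a correlation of 0.3 to 0.7.

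The scope is limited. The primary pain analysis is untouched and both anxiety scores are collected. The statement that only pre-procedural anxiety is named applies to the VAS, since section 11.1 does include a Likert item on satisfaction with anxiety reduction. This should be corrected before the data are analysed, but it does not threaten the trial's main result.

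**What to change.** In section 11.6, replace both anxiety sentences with text such as: *The secondary endpoint is the post-procedure anxiety VAS (mm). Arms will be compared by ANCOVA with the anxiety VAS completed at screening, before the envelope is drawn, as covariate, and the adjusted mean difference will be reported with a 95% CI.* Use the screening score only as covariate and baseline descriptor. State whether the age-subgroup tables also apply to this endpoint.

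Say in section 10.2 whether anxiety is rated once or twice before the procedure. If a second rating is taken after the draw, do not use it as the covariate, because knowledge of the allocation could affect it.

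Any prespecified between-arm contrast on the post-procedure or change score would close the gap. ANCOVA is preferred because it uses data already collected and, under the assumptions above, is more precise than either at every correlation shown. The cost is two or three sentences in section 11.6 and a line in section 10.2. It adds nothing to the burden on participants, and the model is a standard linear one.
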